## 8.2 During Study Therapy

The following will be assessed on each day of radiation therapy after treatment delivery:

- ECOG Performance Status
- Vital Signs
- Adverse Events / SAE
- Concomitant Medications
- Complete Study Time Log

## 8.3 After Study Therapy Completion

After completion of SABR, an optional visit at 6 weeks (+/-14 days), can be performed as per treating physician criteria.

The following will be assessed every three (3) months until 12 month (+/- 28 days) after completion of SABR.

- Physical Examination
- ECOG Performance Status
- CBC
- CMP
- Imaging: CT scan of the chest, abdomen, and pelvis (IV and/or oral contrast as per physician discretion)
- RECIST 1.1
- Adverse Events / SAE
- Concomitant Medications
- FACT-G Survey

Assessments completed as part of the standard of care visits can be used for after treatment visits as long as the test/procedure meets the protocol-required timelines. Note that source documents must identify the standard of care tests/procedures used for this visit and must be reviewed by the investigator for clinical significance. FACT-G and RECIST 1.1, concomitant medications and adverse events evaluation must be performed by a delegated study team member.

**Remote visits:** In the case when an in-person clinic visit is not possible, remote visits will be allowed only for “After Study Therapy” completion visits. When a remote visit occurs, all research specific assessments including the FACT-G questionnaire, concomitant medications, and adverse events will be collected by a delegated study team member.

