**STUDY DESIGN**

This is a single arm, multi-site, feasibility study of single-fraction SMART for primary or metastatic carcinoma involving the lung, liver, adrenal gland, abdominal/pelvic lymph node, pancreas, and/or kidney.

This study will consist of a Baseline period (Day-28 to Day-1), Enrollment, Treatment period (Day 1 up to Day 3), and After treatment visits occurring 6 weeks (optional), 3 months, 6 months, 9 months, and 12 months after completion of Study Therapy.

All patients deemed eligible will receive single-fraction SABR therapy using MRI as image-guidance. A total of 1-10 total lesions may be treated on the study and each lesion will be treated either sequentially or concurrently in one fraction.

FACT-G Survey will be administered at baseline and every visit after completion of Study Therapy.

Safety assessment performed will include collection of Adverse Events (AEs), vital signs, and physical exam, ECOG and laboratory assessments.

CT scan of the Chest, Abdomen and Pelvis will be conducted at baseline, 6 weeks/ optional ( $\pm$  1 week) after study therapy and every 3 months ( $\pm$  1 week) until 12 months ( $\pm$  1 week) after completion of SABR.

All AEs will be collected upon initiation of treatment and for a minimum of 100 days after completion of study treatment or until resolution, whichever occurs later. Any pregnancy that occur at the time of study participation are to be reported.

**Number of Patients (planned):** It is anticipated that approximately 30 patients will be enrolled and treated under this study protocol.

**Sites:** Up to five (5) US sites

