### 2.2 Primary objective

- To determine feasibility and tolerability of SABR delivered in one fraction

Feasibility will be achieved if all are true:

- Successful completion of treatment to each lesion within 3 working days of intended treatment completion
- Successful completion of treatment to each lesion within 90 minutes from the patient entering the treatment room until treatment completion
- Image guidance verification of treatment delivery within 5 mm of the planned delivery
- Tolerability will be achieved if all are true:
  - No greater than 4 of 30 patients experience grade 3 or higher acute toxicity within 90 days of completing SABR
  - No grade 5 toxicity is attributed to SABR

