#### 8.4 Study Calendar

Procedures	Screening (within 28 days prior to Study Therapy)	During Study Therapy 	After Therapy Completion (Optional visit) 6 weeks (+/-14 days)	After Therapy Completion 3m,6m,9m,12m (+/-28 days)
Signed Informed Consent	X			
Medical History/ Prior Cancer History and Therapy	X			
Physical Exam	X		X	X
Vital Signs 	X	X		
ECOG Performance status	X	X	X	X
Concomitant Medication	X	X	X	X
CBC W/ Differential	X		X	X
CMP	X		X	X
Urine pregnancy test 	X			
Imaging 	X		X	X
RECIST 1.1	X		X	X
FACT-G Survey	X		X	X
Adverse Events/SAE 	X	X	X	X
Confirm Eligibility	X			
Study Time log completion 		X		
Off Study 		X	X	X

1. Assessments will be collected each day after receiving study treatment as per the standard of care or per protocol.
2. Vital signs include blood pressure, heart rate, temperature, oxygen saturation via pulse oximetry, weight.
3. Pregnancy test in women of childbearing potential is performed at baseline within 14 days of enrollment.
4. CT scan of the chest, abdomen, and pelvis (IV and/or oral contrast as per physician discretion). Please refer to section 9 of the protocol. If a patient has a contraindication to contrast for a CT scan, then an alternate scan should be considered such as PET/CT or MRI.
5. Only SAEs assessed by the investigator as related to any protocol-specific procedure or therapy will be collected and reported.
6. Study time log should be completed during study treatment visit a as per this protocol Appendix B.
7. Off Study Form to be completed during the 12 months After Therapy Completion Visit or earlier if applicable.

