## 9. TREATMENT RESPONSE EVALUATION

### 9.1 Imaging assessment

Patients should have CT scans of the chest, abdomen, and pelvis at 6 weeks ( $\pm 14$  days) if the six weeks visit is being performed, at 3 months ( $\pm 28$  days), 6 months ( $\pm 28$  days), 9 months ( $\pm 28$  days), and 12 months ( $\pm 28$  days) after completion of SABR delivered on this study, or more often as clinically indicated. IV and/or oral contrast should be used as per treating physician discretion and should be strongly considered if doing so would be critical for clearly visualizing the treated lesion to assess local response.

If a patient has a contraindication to contrast for a CT scan, then an alternate scan should be considered such as PET/CT or MRI.

Treatment response will be evaluated using the Response Evaluation Criteria in Solid Tumors (RECIST) guideline, version 1.1.

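### The CT window differs between the synopsis and section 9.1, and no required adverse-event contact is fixed on or after day 90, when the primary toxicity window closes

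*Combined protocol and SAP*

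**What the plan says.** **CT timing in the synopsis.** Under Study Design, "CT scan of the Chest, Abdomen and Pelvis will be conducted at baseline, 6 weeks/ optional", with 1 week either side for that scan, and then "every 3 months ( $\pm$ 1 week) until 12 months ( $\pm$ 1 week) after completion of SABR". The same section lists the visits themselves without any window: "After treatment visits occurring 6 weeks (optional), 3 months, 6 months, 9 months, and 12 months after completion of Study Therapy".

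**CT timing in the body.** Section 9.1 gives 14 days either side for the 6-week scan, if that visit takes place, and then sets the scans "at 3 months ( $\pm 28$ days), 6 months ( $\pm 28$ days), 9 months ( $\pm 28$ days), and 12 months ( $\pm 28$ days").

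**Visit timing in the body.** Section 8.3 describes "an optional visit at 6 weeks (+/-14 days), can be performed as per treating physician criteria". It then schedules a set of assessments, including both CT and AEs, "every three (3) months until 12 month (+/- 28 days) after completion of SABR". The calendar in section 8.4 heads its last column "After Therapy Completion 3m,6m,9m,12m (+/-28 days") and also marks imaging and AEs there. Section 10 uses the same wide windows for FACT-G.

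**Endpoint.** Section 2.2, repeated in 13.2, makes this a condition of tolerability: "No greater than 4 of 30 patients experience grade 3 or higher acute toxicity within 90 days of completing SABR". Section 11.5 closes the study on the same 90-day count, and section 13.4 requires no more than 4 of 30 patients with grade 3 or higher toxicity for advancement to phase II/III.

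**AE collection.** The synopsis and section 11.1 require AEs to be collected for at least 100 days after treatment. Section 11.1 ties assessment to the schedule of assessments, with extra assessments when clinically indicated.

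**The concern.** There are two issues, linked because CT and AE assessment share a visit.

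First, a site cannot tell whether a scan on day 70 is on schedule or a deviation. It is a deviation under the synopsis and compliant under section 9.1.

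Second, the primary safety endpoint has a fixed end at day 90, but the schedule does not guarantee anyone asks about toxicity at or after that day until the 6-month visit. With the 6-week visit optional, the 3-month visit may be the only required assessment between the treatment day and month 6, and it may take place well before day 90. A grade 3 event after such a visit reaches the database only if the patient or another clinician reports it, or if it is recalled and correctly dated months later. A transient grade 3 laboratory abnormality, which section 11.1 counts as a source of AEs, cannot be recalled if nobody measured it.

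Missed events can only lower the count, so the error runs one way. The same 90-day count serves the primary endpoint and early closure, and the advancement criterion uses the same limit of 4 of 30.

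**Working it through.** **1. The plan's own figure.** Section 13.4 states that at most 4 of 30 patients with grade 3 or higher toxicity has probability 80% at a true rate of 10.5%, and 20% at 21.4%. The exact binomial P(X ≤ 4), n = 30, gives 79.8% and 20.0%. Both are reproduced, and nothing below disputes them.

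**2. CT windows side by side.**

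| Scan | Synopsis | Section 9.1 |
|---|---|---|
| 6 weeks (optional) | ±1 week: day 35 to 49 | ±14 days: day 28 to 56 |
| 3 months (taken as day 91) | ±1 week: day 84 to 98 | ±28 days: day 63 to 119 |

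**3. Earliest compliant 3-month visit.** The documents do not convert 3 months to days, so I take 90 to 92 as the range. Earliest day = 3 months − 28; gap = 90 − earliest day.
- 90 − 28 = day 62, gap 28 days
- 91 − 28 = day 63, gap 27 days
- 92 − 28 = day 64, gap 26 days

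**4. Next required visit.** Taking 6 months as about 182 days, 182 ± 28 gives day 154 to 210. An event on day 90 would be asked about at least 154 − 90 = 64 days later.

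**5. Average gap.** If visits were uniform over day 63 to 119 (57 days), the gaps for days 63 to 89 would run from 27 down to 1 day, and later visits would have none. The mean is (1 + 2 + … + 27)/57 = 378/57 = 6.6 days, or 6.6/90 = about 7% of the endpoint period. The documents say nothing about the actual distribution of visit days.

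**6. Would ±1 week close the gap?** The earliest day becomes 83 to 85, leaving 5 to 7 days. It shrinks the gap but does not remove it.

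**7. Sensitivity of the decision rule (illustration only).** Suppose a fraction c of patients with a qualifying event is recorded. At the plan's unacceptable rate of 21.4%, the chance of passing is P(X ≤ 4) with n = 30 and p = 0.214c.

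| Assumed c | Chance of passing |
|---|---|
| 100% | 20% |
| 90% | 29% |
| 80% | 40% |
| 70% | 53% |

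The capture rates are assumptions. The 70% row is close to a bounding case: every patient seen on day 63, events spread evenly over 90 days, and nothing in the gap ever recovered.

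**The case against.** The strongest reply is that AE collection does not stop at the 3-month visit. It runs for at least 100 days, covers events from any source including patient report, allows extra assessments when indicated, and is followed by another AE assessment at 6 months. Related serious events must be reported within 24 business hours of awareness (section 11.2). This stands. A reader might infer that up to 30% of the endpoint period (27 of 90 days) is unobserved. The documents do not support that: those days lack a required contact, but collection continues through them. What remains is that the 100-day duty has no scheduled contact to discharge it.

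A reader might also take the synopsis to set 1 week for all visits. It does not. The tolerance is attached only to the CT scans, and the visit list carries none. The direct conflict is therefore synopsis against section 9.1, and it reaches sections 8.3 and 8.4 only because they place CT in the same visit. Section 10 concerns FACT-G alone and contradicts nothing in the synopsis.

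A third inference is that the wide window puts nearly half of patients in the gap. Under uniform timing, 27/57 = 47% of visits would fall before day 90, but ±1 week would still give 6/15 = 40%. The share mostly reflects centring the visit near day 90. The wide window mainly lengthens the gap.

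Finally, section 8.3 does not already provide the missing contact. It permits remote visits only when an in-person visit is not possible, not as a call added after a completed early visit.

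**Conclusion.** The point holds in two parts.

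The CT window is wrong as written: the synopsis and section 9.1 give different tolerances for the same scans. That mismatch alone does not change the toxicity endpoint.

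The missing contact at or after day 90 is a weakness in ascertaining the primary endpoint that is cheap to remove. The worst case for one patient is about 4 weeks (26 to 28 days, taking 3 months as 90 to 92 days). The average is about 6.6 days under the uniform-timing assumption. The consequence is possible under-recording that favours a conclusion of tolerable. Its actual size cannot be estimated from the documents, which give neither the timing of grade 3 events nor the expected completeness of later recall. No sample-size or probability statement in section 13.4 needs to change.

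**What to change.** 1. Reconcile the synopsis with sections 9.1, 8.3 and 8.4 so that one set of CT and visit windows applies throughout.
2. State in sections 8.3 and 13.2 that the AE assessment closing the 90-day endpoint must be dated on or after day 90. Either do not allow the AE part of the 3-month visit before day 90, or add a remote AE contact between day 90 and about day 100 for patients seen earlier. The second option also serves the 100-day collection rule.
3. If the remote contact is chosen, amend section 8.3 to permit it, and add it to the section 8.4 calendar.

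Item 1 does not replace item 2, because even the narrower window leaves several days uncovered. The cost is amendment wording and one short phone contact for each patient seen before day 90. A call will not detect a laboratory abnormality that was not measured, so some limitation remains for those events if the call is used instead of a later visit.

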#### 8.4 Study Calendar

Procedures	Screening (within 28 days prior to Study Therapy)	During Study Therapy 	After Therapy Completion (Optional visit) 6 weeks (+/-14 days)	After Therapy Completion 3m,6m,9m,12m (+/-28 days)
Signed Informed Consent	X			
Medical History/ Prior Cancer History and Therapy	X			
Physical Exam	X		X	X
Vital Signs 	X	X		
ECOG Performance status	X	X	X	X
Concomitant Medication	X	X	X	X
CBC W/ Differential	X		X	X
CMP	X		X	X
Urine pregnancy test 	X			
Imaging 	X		X	X
RECIST 1.1	X		X	X
FACT-G Survey	X		X	X
Adverse Events/SAE 	X	X	X	X
Confirm Eligibility	X			
Study Time log completion 		X		
Off Study 		X	X	X

1. Assessments will be collected each day after receiving study treatment as per the standard of care or per protocol.
2. Vital signs include blood pressure, heart rate, temperature, oxygen saturation via pulse oximetry, weight.
3. Pregnancy test in women of childbearing potential is performed at baseline within 14 days of enrollment.
4. CT scan of the chest, abdomen, and pelvis (IV and/or oral contrast as per physician discretion). Please refer to section 9 of the protocol. If a patient has a contraindication to contrast for a CT scan, then an alternate scan should be considered such as PET/CT or MRI.
5. Only SAEs assessed by the investigator as related to any protocol-specific procedure or therapy will be collected and reported.
6. Study time log should be completed during study treatment visit a as per this protocol Appendix B.
7. Off Study Form to be completed during the 12 months After Therapy Completion Visit or earlier if applicable.

## 9. TREATMENT RESPONSE EVALUATION

### 9.1 Imaging assessment

Patients should have CT scans of the chest, abdomen, and pelvis at 6 weeks ( $\pm 14$  days) if the six weeks visit is being performed, at 3 months ( $\pm 28$  days), 6 months ( $\pm 28$  days), 9 months ( $\pm 28$  days), and 12 months ( $\pm 28$  days) after completion of SABR delivered on this study, or more often as clinically indicated. IV and/or oral contrast should be used as per treating physician discretion and should be strongly considered if doing so would be critical for clearly visualizing the treated lesion to assess local response.

If a patient has a contraindication to contrast for a CT scan, then an alternate scan should be considered such as PET/CT or MRI.

Treatment response will be evaluated using the Response Evaluation Criteria in Solid Tumors (RECIST) guideline, version 1.1.

### 9.2 Definitions for disease assessment

- Measurable lesions: Lesions that can be accurately measured in at least one dimension with longest diameter at least 10 mm.
- Malignant lymph nodes: A lymph node will be considered measurable if it measures at least 15 mm in short axis.
- Non-measurable lesions: All other lesions <10 mm or lymph nodes <15 mm in short axis.
- Target lesions: Target lesions should be identified and measured at baseline. Target lesions include measurable lesions up to a maximum of two lesions per organ and up to five lesions in total that are representative of all involved organs. Target lesions should be selected on the basis of their size (lesions with the longest diameter) and are to undergo reproducible repeated measurements. If the largest lesion does not lend itself to reproducible measurement, it should not be considered a target lesion and instead the next largest lesion that can be measured reproducibly should be selected. A sum of the longest diameters for all target lesions will be calculated and reported as the baseline sum diameters. The baseline sum diameters will be used as reference to further characterize any objective tumor regression in the measurable dimension of the disease.
- Non-target lesions: All other lesions (or sites of disease) including any measurable lesions over and above the 5 target lesions should be identified as non-target lesions and should also be recorded at baseline. Measurements of these lesions are not required, but the presence, absence, or in rare cases unequivocal progression of each should be noted throughout follow-up.

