### 5. PATIENT SELECTION

#### 5.1 Inclusion criteria

1.  $\geq 18$  years of age at the time of study enrollment
2. Biopsy-confirmed primary or metastatic carcinoma with involvement of the lung, liver, adrenal gland, pancreas, kidney, and/or abdominal/pelvic lymph node that would receive SABR
3. Any lesion that would receive SABR is no larger than 5 cm in greatest dimension
4. 1-10 total lesions that would receive SABR
5. If multiple lesions are treated, they must be at least 3 cm apart
6. Eastern Cooperative Oncology Group (ECOG) performance status of 0-2
7. Life expectancy at least 6 months
8. Women of childbearing potential and men must agree to use adequate contraception (hormonal or barrier method of birth control) prior to study entry and for the duration of study participation. Abstinence is acceptable if preferred by patient. Should a woman become pregnant or suspect she is pregnant while participating in this study, she must inform her treating physician immediately.

9. Patients receiving hormonal therapy or immunotherapy such as immune checkpoint inhibitor that had begun at least 4 weeks prior to SABR will be allowed.

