## 9.3 Definitions of Disease Response

Definition of response in target lesions:

- **Complete Response (CR):** Disappearance of all target lesions
- **Partial Response (PR):** At least a 30% decrease in the sum of the diameters of target lesions, taking as reference the baseline sum diameters
- **Local Progressive Disease (LPD):** At least a 20% increase in the sum of the diameters of target lesions compared to baseline sum of target lesions, taking as reference the smallest sum on study (this includes the baseline sum if that is the smallest on study). The sum must also demonstrate an absolute increase of at least 5 mm in addition to the relative increase of 20%.
- **Distant Progressive Disease (DPD):** The appearance of at least 1 new lesion.
- **Stable Disease (SD):** Neither sufficient decrease to qualify as a PR or sufficient increase to qualify as PD, taking as reference the smallest sum diameters while on study.

Definition of response in non-target lesions:

- **Complete Response (CR):** Disappearance of all target lesions
- **Progressive Disease (PD):** Appearance of one or more new lesions and/or unequivocal progression of existing non-target lesions
- **Incomplete Response/Stable Disease (SD):** Persistence of one or more non-target lesions

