#### 13.3 Secondary objectives

1-year local control (LC) will be assessed according to RECIST 1.1 criteria and will be estimated using the Kaplan-Meier method along with the corresponding 95% confidence interval from the time of study treatment

1-year overall survival (OS) will be estimated using the Kaplan-Meier method along with the corresponding 95% confidence interval from the time of study treatment

The proportion of patients who experience acute grade 3 or higher toxicity attributable to SABR will be determined along with the corresponding 95% confidence interval. For patients receiving SABR to multiple lesions, acute toxicity will be determined from the date of the initiation of SABR.

Patient-reported quality of life will be determined using the FACT-G survey instrument prior to and after SABR.

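### Irradiated lesions that are non-target (too small, or beyond the target cap) have no rule linking their progression to 1-year local control

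*Combined protocol and SAP*

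**What the plan says.** **Eligibility (section 5.1).** The size criterion is an upper limit only: "Any lesion that would receive SABR is no larger than 5 cm in greatest dimension". The number treated is "1-10 total lesions that would receive SABR". Neither section 5.1 nor section 5.2 sets a minimum size or requires measurable disease. Sections 7.2 and 8.1 require a RECIST evaluation at screening, which is not the same as requiring a measurable lesion.

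**Lesion classes (section 9.2).** Measurable lesions are "Lesions that can be accurately measured in at least one dimension with longest diameter at least 10 mm". For nodes, "A lymph node will be considered measurable if it measures at least 15 mm in short axis". The remainder are described as "Non-measurable lesions: All other lesions <10 mm or lymph nodes <15 mm in short axis". Targets are chosen from measurable lesions, at most two per organ and five in total, and the choice is not tied to whether a lesion was irradiated. Everything else is non-target: it is recorded at baseline, need not be measured, and is followed lesion by lesion for presence, absence or unequivocal progression.

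**Progression (section 9.3).** Local progressive disease is "At least a 20% increase in the sum of the diameters of target lesions compared to baseline sum of target lesions", with an absolute rise of at least 5 mm as well. For non-target lesions, progressive disease is "Appearance of one or more new lesions and/or unequivocal progression of existing non-target lesions".

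**Endpoint (section 13.3).** "1-year local control (LC) will be assessed according to RECIST 1.1 criteria", estimated by Kaplan-Meier from the time of study treatment. No other event definition is given.

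**The concern.** Local control is a question about the lesions that were irradiated, and section 9.1 shares that aim when it speaks of seeing the treated lesion clearly enough to judge local response. The definitions that follow are built on target status instead. A small lung or liver lesion, or an abdominal or pelvic node under 15 mm in short axis, may be treated on study and yet never enter the only quantity that defines local progression.

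An analyst then has two written rules to choose from. Local progressive disease cannot see the lesion. Non-target progressive disease can see it, but does not separate its growth from the appearance of disease elsewhere. The same scans could yield different local control results depending on a choice that the plan does not make in advance.

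**Working it through.** The plan states no figure for local control, its precision or the lesion-size mix, so there is none to reproduce. The check is a trace through the definitions, followed by an illustration of size.

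**Trace: which irradiated lesions are non-target?**

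1. *Below threshold.* A non-nodal lesion under 10 mm or a node under 15 mm in short axis meets section 5.1, which has only the 5 cm ceiling. Under section 9.2 it is non-measurable and so cannot be a target.
2. *Beyond the cap.* Up to 10 lesions may be treated and at most 5 can be targets, so with 10 treated at least 10 − 5 = 5 are non-target. With three measurable lesions in one organ, 3 − 2 = 1 is non-target. These lesions are measurable but still lie outside the sum.

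**Trace: what happens when such a lesion grows?**

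| Rule applied literally | Treated non-target lesion grows | New lesion elsewhere, treated lesion stable |
|---|---|---|
| Local progressive disease (target sum) | No local failure recorded | No local failure recorded |
| Non-target progressive disease | Event, if judged unequivocal | Event |

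The correct entries for local control are failure in the first column and no failure in the second. Each rule gets one column wrong. If a patient has no target lesion at all, the sum does not exist, and the overall-response table in section 9.4 has no row for that patient.

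**Illustration of size.** Inputs: N = 30 (section 13.4). Assumed: true 1-year local control LC of 80%, with 70% as a second value; a share u of patients with no irradiated lesion among the targets; the same failure rate in those patients as in the others; no censoring; the patient as the unit.

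*Scored by local progressive disease, so never failing:* estimated LC = LC + (1 − LC) × u, a shift of (1 − LC) × u. The standard error is √(LC(1 − LC)/30).

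- LC = 0.80: SE = √(0.16/30) = 0.073.
  - u = 1/30: shift 0.20/30 = 0.0067, about 0.7 points; 0.0067/0.073 = 0.09 SE.
  - u = 0.10: shift 0.020, or 2.0 points; 0.020/0.073 = 0.3 SE.
- LC = 0.70: SE = √(0.21/30) = 0.084.
  - u = 1/30: shift 0.30/30 = 0.010, or 1.0 point; 0.010/0.084 = 0.12 SE.
  - u = 0.10: shift 0.030, or 3.0 points; 0.030/0.084 = 0.36 SE.

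*Scored by non-target progressive disease:* the error runs the other way. Each locally controlled patient counted as failed because of a new lesion lowers the estimate by 1/30 = 3.3 points. The rate of new lesions is not given, so no expected shift can be computed.

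*Chance of meeting the problem at all:* P(at least one such patient in 30) = 1 − (1 − u)^30, which is 79% at u = 5% and 96% at u = 10%.

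The shift formula covers only patients with no irradiated lesion among the targets. Patients with some treated lesions inside the sum and some outside it add to the missed failures by an amount the documents do not allow one to size.

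**The case against.** The strongest reply is that the plan does follow these lesions. Section 9.2 has each non-target lesion recorded at baseline and its unequivocal progression noted, section 9.3 gives non-target lesions a response scale, and section 13.3 invokes RECIST 1.1 as a whole, not local progressive disease alone. A reader might infer that a patient with only small irradiated lesions cannot be scored for local control at all. The documents do not support that: growth can be recorded qualitatively. What is missing is the sentence that makes such growth a local failure.

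A reader might also infer that distant disease will necessarily be counted as local failure. That goes too far as well. Section 9.3 labels a new lesion as distant progression, although under the target-lesion heading, and section 9.4 keeps new lesions in their own column, so the data collected can separate the two. The literal non-target rule nevertheless pools them, and nothing tells the analyst to set that rule aside.

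Nor do the documents say that affected patients stay in the risk set as controlled; they could be treated as unevaluable or censored. Never-failing scoring is one literal reading, used here as an assumption. Likewise, nodes being one of six eligible sites does not make a sixth of patients affected: that would need equal accrual by site and only sub-threshold nodes in every nodal patient.

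Finally, local control is secondary. The sample size is pragmatic, and neither the advancement criteria in section 13.4 nor the closure rule in section 11.5 uses it. That stands, and it limits the weight of the point.

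**Conclusion.** The point holds as a gap in the definition of a secondary endpoint. Eligibility admits irradiated lesions that section 9.2 makes non-target, by size or by the cap, and no rule carries progression of such a lesion into 1-year local control. It is more than a missing detail, because following either written rule literally can give a wrong result: one omits local failures, the other can add distant ones.

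The effect is probably modest but cannot be fixed from the documents. At an assumed true local control of 80% with never-failing scoring, it runs from about 0.7 points for one affected patient in 30 to 2.0 points for an assumed 10% share, both well inside one standard error. Feasibility, tolerability and the sample size of 30 are unaffected. The plan should still be amended, since the remedy is cheap and the choice is best made before the scans are read.

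**What to change.** Amend sections 9.2, 9.3 and 13.3, and the matching lines of the protocol summary, as follows.

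- Measure every lesion irradiated on study at baseline and at each protocol CT, whatever its RECIST class.
- Define local failure per irradiated lesion. For a lesion measurable at baseline, including one left out of the targets by the cap: growth of at least 20% and at least 5 mm from that lesion's own nadir. For a lesion non-measurable at baseline: unequivocal progression of that lesion, supported by the recorded measurements. Requiring a small lesion to reach the measurable size before it can fail is not advised: a lesion growing from 4 mm to 9 mm would not count, although the existing qualitative rule could catch it.
- State that new lesions elsewhere and growth of unirradiated lesions are not local failures.
- Report how many patients had no measurable irradiated lesion, and give 1-year local control with and without them.

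The cost is protocol and SAP wording plus extra measurements on CTs already scheduled; no additional scans or patients are needed. The downsides are that measurements of small lesions are less precise and that the local control estimate may come out slightly lower.
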